7.1.1 CDISC Compliance

The trial database will be CDISC compliant which means that the clinical database will be processed and generated according to CDISC standard. The database will be validated against SDTM and ADaM Validation rules using Pinnacle 21.

The following CDISC documentation will be generated:

- SDTM Data Definition Specification (also referred to as a Define -XML)
 - Define-XML transmits metadata that describes any tabular dataset structure and supports the interchange of dataset metadata for clinical research applications in a machine-readable format.
- ADaM Data Definition Specification (also referred to as a Define -XML)
 - Define-XML transmits metadata that describes any tabular dataset structure and supports the interchange of dataset metadata for clinical research applications in a machine-readable format.
- Annotated Electronic Case Report Form (eCRF)
 - Links the data collection fields used to capture trial data to the corresponding variables in the trial database. It enables the user to understand how the trial data were collected and to trace back from trial analysis results to the origin where it was collected.
- SDTM Reviewers' Guide
 - Intended to provide additional context and act as a single point of orientation for the SDTM datasets.
- ADaM Reviewers' Guide
 - Provides regulatory agency reviewers an orientation to the submitted analysis data in a consistent way and usable format.

7.2 Database modeling of trial design

The trial design is mapped to a SDTM trial design model containing the following structural components:

EPOCH: An interval of time in the planned conduct of a trial. An epoch is associated with a purpose (e.g., screening, randomisation, treatment, follow-up), and applies across all arms of the trial. Trial epochs follow a controlled terminology to represent the different trial parts (e.g., SCREENING, TREATMENT [X], FOLLOW-UP)

[figure not shown]
ELEMENT: Building blocks used to build up the entire trial length for all subjects. Information on ELEMENTs is extracted from the trial design and schedule of events in the protocol. ELEMENTs are defined to span the entire trial without gaps. One EPOCH may contain one or several ELEMENTs. All ELEMENTs must have transition rules in accordance with the protocol to determine start and end.

ARM: Subjects are allocated to trial arms depending on the trial design, either by randomisation or other allocation processes defined in the trial protocol. ARMs are defined as the total number of planned ways a subject can go through the trial (unique combination of trial ELEMENTs). All ARMs must contain a unique sequence of ELEMENTs.

VISIT: Trial visits are defined as planned timepoints during the trial where trial data is collected. A visit can be performed in clinic, by off-site contact with trial personnel (phone call, video conference or similar), or by subject initiated recordings of data. The visit schedule is extracted from protocol and eCRF design.

A schematic representation of the SDTM trial design is presented in Figure 1.

Figure 1 Schematic representation of the SDTM trial design

8 STATISTICAL DELIVERABLES

The following items will be delivered:

- Statistical analyses, summary tables, listings and figures as described under Section 10
- Clinical trial database delivered as a SAS-export file (SDTM and ADaM) and Excel files (ADaM)
- Define -XML for SDTM
- Define -XML for ADaM
- Annotated eCRF
- SDTM Reviewer's Guide
- ADaM Reviewer's Guide

9 STATISTICAL METHODOLOGY

In general, data will be presented in tables with the number of observations, arithmetic mean, standard deviation (SD), median, minimum and maximum value for continuous data. In addition, 95% confidence intervals (CIs) will be added for ECG, vital signs and safety laboratory data. Categorical data will be presented with counts and percentages. All collected data will be listed by subject and dose group, except for data pertaining to the exploratory endpoints which will be reported elsewhere. Data is generally presented by dose group.

Details on statistical analyses and descriptive summaries are specified below.

All statistical analyses and descriptive summaries will be performed using SAS version 9.4 (SAS institute, Cary, NC).

PK parameters will be calculated by Non-Compartmental Analysis (NCA) using the software Phoenix WinNonlin® version 8.3 (Certara, U.S.A).

9.1 Analysis of the primary endpoints

9.1.1 *Pharmacokinetic analysis*

The following non-compartmental plasma PK parameters will be determined/calculated during the trial conduct:

Plasma IRL757:

- T_{max} – Time to reach C_{max}
- C_{max} – The maximum observed plasma concentration
- $AUC_{0\text{-last}}$ – Area under the plasma concentration versus time curve (AUC) from timepoint 0 to t , where t represents the timepoint of the last detectable plasma concentration
- $AUC_{0\text{-}24h}$ – AUC from timepoint 0 to 24 h
- $AUC_{0\text{-}inf}$ – AUC from timepoint 0 extrapolated to infinity
- CL/F – Apparent clearance
- V_z/F – Apparent volume of distribution associated with terminal phase
- Λ_{z} – Eliminate rate constant associated with the terminal phase
- $T_{1/2}$ – Terminal plasma elimination half-life

For the 3 main metabolites following PK parameters will be determined/calculated (if possible):

- T_{max}
- C_{max}
- $AUC_{0\text{-last}}$
- $AUC_{0\text{-}24h}$
- $AUC_{0\text{-}inf}$
- Λ_{z}
- $T_{1/2}$

Parameters that are only presented in listings

- Lambda_z lower – Lower limit on time for values to be included in the calculation of Lambda_z
- Lambda_z upper – Upper limit on time for values to be included in the calculation of Lambda_z
- No points lambda_z – Number of points used in computing lambda_z
- Span – The ratio between the interval used for determination of lambda_z and the terminal T_{1/2}
- Rsq adj – Goodness of fit statistic for the terminal phase, adjusted for the number of points used in the estimation of lambda_z.
- T_{last} – Time of last observed plasma concentration
- AUC_{extr%} – Percentage of AUC_{0-inf} due to extrapolation from T_{last} to infinity
- AUC_{0-48h} – (AUC) from timepoint 0 to 48 h

The following non-compartmental urine PK parameters will be calculated during the trial conduct:

- A_e – Amount IRL757 excreted unchanged (IRL757 and major metabolites)
- F_e – Fraction of dose excreted in urine (only IRL757)
- CL_{renal} – Renal clearance (only IRL757)

Following units will be used:

- Time: h
- Concentration: umol/L
- AUCs: h*umol/L
- Extrapolated AUC and F_e: %
- Lambda_z: /h
- Apparent Clearance: L/h
- Apparent Volume of distribution: L
- A_e: umol and/or mg

Non-compartmental analysis will be based on the actual sampling times recorded during the trial. For the purpose of calculating PK parameters, concentrations below lower limit of quantification (LLOQ) occurring before C_{max} will be treated as zero. Concentrations below LLOQ occurring after C_{max} will be omitted from the analysis.

T_{max}, T_{last}, and C_{max} will be based on the observed plasma concentration data.

All AUC will be assessed by integration of the plasma concentration vs time curve using linear interpolation for increasing plasma levels and logarithmic interpolation for decreasing plasma levels (Linear Up-Log Down method).

AUC_{0-last} will be calculated from time 0 to the time t of the last detectable plasma concentration.

For AUC_{0-inf} the area will be calculated to the last timepoint showing a measurable plasma concentration and then extrapolated to infinity using the concentration in the last quantifiable sample and lambda_z.

$$AUC_{0-inf} = AUC_{0-last} + \frac{C_{last}}{\lambda_{az}}$$

Partial AUC will be derived according to specified time windows/dosing interval, if the end time of the interval does not occur at an actual timepoint either linear interpolation or extrapolation will be used for derivation of the partial AUC. Extrapolation, using λ_{az} , will only be used if the end time of specified interval occur after last detectable plasma concentration.

Formulas for calculation of AUC

- Linear trapezoidal rule:

$$AUC|_{t1}^{t2} = \delta t \times \frac{C_1 + C_2}{2}$$

- Logarithmic trapezoidal rule:

$$AUC|_{t1}^{t2} = \delta t \times \frac{C_2 - C_1}{\ln\left(\frac{C_2}{C_1}\right)}$$

where t = time, c = concentration, $\delta t = t_2 - t_1$.

Formulas for interpolation (to find C^* at time t^* for $t_1 < t^* < t_2$)

- Linear interpolation rule:

$$C^* = C_1 + \left| \frac{t^* - t_1}{t_2 - t_1} \right| (C_2 - C_1)$$

- Logarithmic interpolation rule:

$$C^* = \exp \left(\ln(C_1) + \left| \frac{t^* - t_1}{t_2 - t_1} \right| * (\ln(C_2) - \ln(C_1)) \right)$$

where t = time, c = concentration

λ_{az} , the first order rate constant associated with the terminal portion of the curve will be determined by lin-logarithmic regression of the terminal elimination phase of individual plasma concentration vs time curves. Determination of λ_{az} requires identification of a sufficiently linear terminal phase (as determined by visual inspection of the lin-log plasma concentration vs time plot with the regression line) consisting of at least 3 terminal concentration values (not including C_{max}). If this is not achieved, λ_{az} and its dependent PK parameters will not be reported for that profile.

In the following cases, lambda_z dependent PK parameters will be flagged in listings as potentially unreliable:

- Lambda_z estimation is based on a period of less than 1.5 times the resulting T_{1/2}.
- The Rsq adjusted value of the regression line is < 0.85.
- The estimated % extrapolated AUC is > 20% ((AUC_{0-inf}-AUC_{0-last} / AUC_{0-inf})*100).

T_{1/2} will be calculated accordingly:

$$T_{1/2} = \frac{\ln (2)}{\lambda_z}$$

Span will be calculated accordingly:

$$Span = \frac{\lambda_z \text{ upper} - \lambda_z \text{ lower}}{T_{1/2}}$$

CL will be calculated accordingly:

$$\frac{CL}{F} = \frac{Dose}{AUC_{0-inf}}$$

V_z will be calculated accordingly:

$$\frac{V_z}{F} = \frac{Dose}{\lambda_z * AUC_{0-inf}}$$

A_e will be calculated accordingly:

$$A_e = \sum_{i=1}^n v_i * c_i$$

Let v be the volume of urine and c the concentration of drug in urine, the product of v and c for one interval (i) represent A_e. The A_e over 0-48 hours is the sum of all intervals. The weight of the collected urine fractions will be calculated assuming a urine density of 1.00 g/mL.

CL_{renal} will be calculated accordingly:

$$CL_{renal} = \frac{A_e}{AUC_{0-48h}}$$

If there is a confirmed dosing error during the trial, the pharmacokinetic data for that period will only be included in the listings but excluded from descriptive and statistical analyses. In case of missed blood samples, potential impact on PK parameters will be assessed for each individual case. PK parameters with a high degree of uncertainty due to missing samples (e.g., multiple samples missing around C_{max}) will be flagged as unreliable in the report and may in rare cases be excluded from summary tables, descriptive statistics, and statistical analysis.

Descriptive statistics for the PK parameters will be presented by dose group using summary statistics with the number of measurements (n), arithmetic mean, SD, as well as median, minimum and maximum values. For all applicable PK parameters, the geometric mean and geometric coefficient of variation (CV%) will be presented. For the parameter T_{max} , the number of observations, and median, minimum and maximum values will be presented only.

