CONFIDENTIAL

A single-centre, open-label, phase I trial evaluating the pharmacokinetics of single ascending oral doses of IRL757 in healthy elderly volunteers.**PROTOCOL SYNOPSIS**

Version: 2.1
Version date: 02-OCT-2024
Superseded version: Not applicable
Sponsor: Integrative Research Laboratories Sweden AB (IRLAB)
Product: IRL757 [REDACTED]
Trial Number(s): IRL757C002
EU trial no: 2024-515124-36-00
NCT no: NCT06699628

Integrative Research Laboratories Sweden AB (IRLAB)
[name]
[name]
SWEDEN
[contact]

TRIAL SYNOPSIS

Trial Title	
A single-centre, open-label, phase I trial evaluating the pharmacokinetics of single ascending oral doses of IRL757 in healthy elderly volunteers.	
Trial code	EU trial no
IRL757C002	2024-515124-36-00
Trial period	Phase of development
Estimated date of first subject enrolled: Q3 2024	Phase I
Estimated date of last subject completed: Q4 2024	
Trial background	
IRL757 [REDACTED] is a novel small molecule compound developed for the treatment of apathy in neurodegenerative disorders. This is a trial of IRL757 with the aim to study safety, tolerability and PK following single oral doses to healthy elderly volunteers.	
Trial design and trial population	
An open label single oral dose trial in elderly healthy volunteers.	
Objectives	
Primary objective: 
 To determine the single oral dose pharmacokinetic (PK) characteristics of IRL757 and its 3 main metabolites in healthy elderly volunteers. 	
Secondary objectives: 
 To evaluate the safety and tolerability of IRL757 after single oral dosing in healthy elderly volunteers. 	
Exploratory objective: 
 To characterize the metabolite profile in plasma and urine of healthy elderly volunteers. 	
Endpoints	
Primary endpoints: PK assessments 
 AUC_{0-t}, AUC_{0-24h}, $AUC_{0-\infty}$, C_{max}, T_{max}, λ_{z}, $T_{1/2}$, amount excreted in urine (Ae), CL/F, V_z/F, fraction of the dose excreted in urine (Fe) (for IRL757), renal clearance CL_R. Dose proportionality after single doses based on AUC_{0-t}, $AUC_{0-\infty}$ and C_{max}. 	
Secondary endpoints: Safety assessments 
 Frequency, seriousness and intensity of Adverse Events (AEs) Physical examination 	

- Columbia-Suicide Severity Rating Scale (C-SSRS)
- Electrocardiogram (ECG) recordings

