4.2 Trial objectives and endpoints

Table 1 Trial objectives and endpoints

| Objectives | Endpoints | Assessments | Analyses | Data display plan (DDP) |
|---|---|--|---|---|
| Primary objective | Primary endpoints | | | |
| To determine the single dose PK characteristics of IRL757 and its 3 main metabolites in elderly healthy volunteers. | 
IRL757 and 3 main metabolites: Area under the plasma concentration-time curve AUC_{0-t}, AUC_{0-24}, $AUC_{0-\infty}$, maximum concentration (C_{max}), time to maximum concentration (T_{max}), terminal elimination rate constant (λ_{z}), terminal half-life ($T_{1/2}$), amount excreted in urine (A_e)
 
IRL757 only: total apparent clearance of drug from plasma (CL/F), volume of distribution (V_z/F), fraction of the dose excreted in urine (F_e), renal clearance CL_R.
 | PK plasma and urine sampling | Descriptive statistics, Section 9.1.1 | Sections 10.2.2.1, 10.3.1.1 |
| | 
IRL757 and metabolites M5, M7: Dose proportionality after single oral doses based on AUC_{0-t}, $AUC_{0-\infty}$ and C_{max}
 | | Dose proportionality analysis, Section 9.1.1.1 | Section 10.3.1.2 |
| Secondary objective | Secondary endpoints | | | |
| To evaluate the safety and tolerability of IRL757 after single oral dosing in healthy elderly volunteers. | 
Frequency, seriousness and intensity of adverse events (AEs).
 
Physical examination
 
Electrocardiogram (ECG) recordings
 
Vital signs
 
Safety laboratory measurements
 
Columbia-Suicide Severity Rating Scale (C-SSRS)
 | 
AE reporting and questioning
 
Physical examinations
 
12-lead safety ECG
 
Blood pressure, heart rate, respiratory rate, body temperature
 
Blood sampling for haematology, clinical chemistry and coagulation
 
C-SSRS questionnaire
 | 
Descriptive statistics, Section 9.2.1
 
Descriptive statistics, Section 9.2.2
 
Descriptive statistics, Section 9.2.3
 
Descriptive statistics, Section 9.2.4
 
Descriptive statistics, Section 9.2.5
 
Listings, Section 9.2.6
 | 
Section 10.2.3.1
 
Section 10.2.3.2
 
Section 10.2.3.3
 
Section 10.2.3.4
 
Section 10.2.3.5
 
Section 10.4
 |
| Exploratory objective | Exploratory endpoints | | | |

| Objectives | Endpoints | Assessments | Analyses | Data display plan (DDP) |
|--|--|-----------------------------------|--|-------------------------|

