6 CHANGES FROM THE CLINICAL TRIAL PROTOCOL

Changes to the planned analyses and the timing of these are summarised in Table 3.

Table 3 Changes in the planned statistical analyses

| Change category | Timing of change | Description of change | Reason for change |
|--|------------------|--|--|
| Change in the SAP compared to the protocol | Prior to DBL | Added frequency tables for safety laboratory interpretations | To provide a better overview of the safety laboratory data. |
| Change in the SAP compared to the protocol | Prior to DBL | Removed dose proportionality for metabolite M1 | Not relevant with dose proportionality for M1 due to [REDACTED] polymorphism |

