Table PP 6 Renal PK parameters of 3 main metabolites of IRL757 (Pharmacokinetic analysis set)

| Assessment (unit) | Metabolite | IRL757 [REDACTED] (N=6) | IRL757 [REDACTED] (N=6) |
|-------------------|--------------------------|-------------------------------|-------------------------------|
| Ae (unit) | M1 | | |
| | n | xx | xx |
| | Mean (SD) | x.xx (x.xx) | x.xx (x.xx) |
| | Median (Min, Max) | x.xx (x.x, x.x) | x.xx (x.x, x.x) |
| | Geometric Mean (geo CV%) | x.xxx (x.x%) | x.xxx (x.x%) |
| | M5 | | |
| | n | xx | xx |
| | Mean (SD) | x.xx (x.xx) | x.xx (x.xx) |
| | Median (Min, Max) | x.xx (x.x, x.x) | x.xx (x.x, x.x) |
| | Geometric Mean (geo CV%) | x.xxx (x.x%) | x.xxx (x.x%) |
| | M7 | | |
| | n | xx | xx |
| | Mean (SD) | x.xx (x.xx) | x.xx (x.xx) |
| | Median (Min, Max) | x.xx (x.x, x.x) | x.xx (x.x, x.x) |
| | Geometric Mean (geo CV%) | x.xxx (x.x%) | x.xxx (x.x%) |

Data based on [population]. n: Number of observations. n: Number of observations. BLQ: Below lower limit of quantification. SD: Standard deviation. CV%: Coefficient of variation described as percentage. Geo CV%: Geometric coefficient of variation described as percentage calculated using log-transformed standard deviation. NC: Not calculated - number of evaluable observations less than 3 or more than half of the observations are BLQ. NA: Not available - no evaluable observations. SAS program: [PROGRAM NAME].sas.
 Dataset version: ADXX YYYY-MM-DDTHH:MM:SS. Run by: [USERNAME] YYYY-MM-DDTHH:MM:SS. EDC data extracted: YYYY-MM-DDTHH:MM:SS.

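### Does the SAP drop a planned endpoint by limiting renal clearance to the parent drug?

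*SAP*

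**What the plan says.** The protocol synopsis gives the primary PK endpoints as a single list of twelve parameters, under an objective covering IRL757 and its three main metabolites. Near the end it reads "fraction of the dose excreted in urine (Fe) (for IRL757), renal clearance", followed by the symbol CL_R. That is the only analyte qualifier in the list.

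SAP Table 1 (Section 4.2) splits the list in two. Eight parameters, from the AUCs to the amount excreted (Ae), apply to the parent and the three metabolites. Four are confined to the parent: CL/F, Vz/F and then "fraction of the dose excreted in urine (F_e), renal clearance CL_R". Section 9.1.1 repeats the restriction: "Renal clearance (only IRL757". The displays follow it. Table PP 3 gives Ae, Fe and CL_R for the parent, while "Table PP 6 Renal PK parameters of 3 main metabolites of IRL757 (Pharmacokinetic analysis set" contains Ae only.

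Section 9.1.1 defines CL_R as Ae divided by AUC0-48h. On the numerator it says "The A_e over 0-48 hours is the sum of all intervals". The denominator falls under "Parameters that are only presented in listings", with no analyte named.

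SAP Table 3 (Section 6) records two changes from the protocol. The only PK one is "Removed dose proportionality for metabolite M1".

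**The concern.** Read literally, the synopsis puts CL_R outside the parent-only qualifier, so it would apply to all four analytes. The SAP then reports it for one of four. Up to 3 metabolites × 12 subjects = 36 subject-level values go unsummarised, and nothing says why. The SAP did log and explain another narrowing of metabolite scope, the M1 dose-proportionality change, so its silence here stands out.

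CL_R also differs from its parent-only neighbours. CL/F and Vz/F contain the administered dose, and Fe is a fraction of it, so none of these carries over directly to a metabolite. Ae/AUC0-48h has no dose term. Urine is collected in fractions to 48 h and plasma is sampled to 48 h, so no new sample or assay would be needed. If the synopsis did intend metabolite CL_R, a primary endpoint would have been narrowed without record, and its variability between elderly subjects would not appear in any table.

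**Working it through.** **1. The two lists side by side**

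| Position in synopsis list | Parameters | Qualifier in synopsis | Scope in SAP Table 1 |
|---|---|---|---|
| 1–8 | AUC0-t, AUC0-24h, AUC0-∞, Cmax, Tmax, λz, T1/2, Ae | none | parent and 3 metabolites |
| 9–10 | CL/F, Vz/F | none | parent |
| 11 | Fe | parent | parent |
| 12 | CL_R | none | parent |

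The order is the same in both documents. The SAP cuts the list once, after Ae. If the absence of a qualifier made a parameter apply to metabolites, CL/F and Vz/F would apply as well. Their SAP formulas, Dose/AUC0-inf and Dose/(λz × AUC0-inf), make that reading implausible. The parenthesis is therefore not a reliable marker of scope for the parameters around it.

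**2. Could metabolite CL_R be computed?**

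CL_R = Ae/AUC0-48h, in µmol ÷ (h·µmol/L) = L/h. Metabolite Ae over 0–48 h is planned (Table PP 6), and metabolite plasma concentrations are planned (Table PC 2) with sampling to 48 h. So it is feasible, with gaps. Extrapolation by λz "will only be used if the end time of specified interval occur after last detectable plasma concentration", and λz is not reported without an adequate terminal phase. Some profiles could have no value.

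**3. What the planned tables already give**

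In the same subjects, the geometric mean of a ratio equals the ratio of the geometric means:

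GM(CL_R) = GM(Ae)/GM(AUC0-48h).

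Table PP 6 gives GM(Ae). Table PP 4 gives GM(AUC0-last), which can stand in approximately for AUC0-48h. The typical value is therefore approximable.

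**4. What they do not give**

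On the log scale,

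var(ln CL_R) = s₁² + s₂² − 2ρs₁s₂, with s² = ln(1 + CV²) and CV = √(exp(var) − 1).

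The documents give no variability, so equal CVs for Ae and AUC0-48h are assumed. At 40%, s² = ln(1.16) = 0.1484. Then ρ = 0 gives var = 2 × 0.1484 = 0.297 and a CV of 58.8%; ρ = −1 gives var = 4 × 0.1484 = 0.594 and a CV of 90.0%.

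| Assumed CV of each | ρ = 1 | ρ = 0.5 | ρ = 0 | ρ = −1 |
|---|---|---|---|---|
| 30% | 0% | 30% | 43.4% | 64.2% |
| 40% | 0% | 40% | 58.8% | 90.0% |
| 50% | 0% | 50% | 75.0% | 120.1% |

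The marginal tables do not determine ρ, so they do not determine the spread of CL_R. But each row covers every correlation from +1 to −1. It shows that the quantity is not identified from the tables; it says nothing about what this trial is likely to produce.

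**5. Does anything depend on it?**

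The one declared conclusion in the SAP is dose proportionality (Section 9.1.1.1). It uses AUC0-t, AUC0-inf and Cmax, with no urine parameter. No sample size was calculated, and Section 9.5 plans no formal interim analysis. The remaining PK output is descriptive.

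**The case for a change.** The best case for acting is that the SAP keeps a log for exactly this kind of difference, used it for M1, and did not use it here. Either the restriction is a change and belongs in Table 3, or it is a clarification and the synopsis could be aligned. Each costs about one line, and metabolite CL_R itself would add twelve statistic rows (3 × 4) to Table PP 6. The tables also cannot supply the spread: two sets of six subjects with identical Ae and AUC summaries can give very different CL_R distributions. Take Ae of 5, 7, 9, 11, 14, 18 and AUC of 2, 3, 4, 5, 6.5, 9. Paired in order, CL_R has geometric mean 2.23 and geometric CV 7.5%; paired in reverse, it has the same mean and a CV of 132%.

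The textual observation stands: the synopsis wording is ambiguous and Table 3 is silent. The algebra stands too, although reversed pairing is a constructed extreme. The step from ambiguity to a lost endpoint does not stand. It needs the position of the parenthesis to be decisive for CL_R while being ignored for CL/F and Vz/F. Only the synopsis is available, and the SAP refers to the full protocol for details, so a departure cannot be shown.

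The loss is also limited. Listing 16.2.5-3 gives PK parameters by subject, and the ADaM data are delivered as SAS and Excel files, so anyone wanting metabolite CL_R could derive it. One reservation remains: the SAP does not say that AUC0-48h will be listed for the metabolites, so it might have to be computed from the listed concentrations.

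**Conclusion.** No change to the plan is called for. The synopsis is loosely worded, and the SAP resolves it consistently: CL_R is for the parent in Table 1, Section 9.1.1 and Table PP 3, and is left out of Table PP 6. An analyst following the SAP cannot mistake the scope, and no reported number, rule or conclusion comes out wrong.

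What is forgone is a descriptive summary of metabolite CL_R spread in about six subjects per dose group. The centre of that distribution is approximable from planned tables, and no decision uses the spread. Adding it would be an optional extra, with some values expected to be missing. Aligning the synopsis or adding a line to Table 3 would write down a scope the SAP already states and would change no result.

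This rests on the synopsis being the only protocol text available. If the full protocol expressly named CL_R as a metabolite endpoint, the restriction would be an unlogged change. Nothing in the documents shows that. The CV figures rest on assumed inputs and are not needed for the conclusion.
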